C. For Arm D patients (i.e., from Step 1 Arm A or B patients), information taken from T2 (see Sec. 6.1) will be used to pre-populate T0SS, and only the remaining items in T0SS will need to be completed. The “Uncertainty” and “Perceived Utility of Genetic Testing” assessments in T2 are exceptions, and must be completed in T0SS for all patients. For Arm E patients (i.e. those from Step 1 Arm C), the entire T0SS will be completed as the baseline survey.

Assessment Schedule:

Secondary Genetic Counseling Substudy (Step 2)				
Assessment ^A	T0SS	T1SS	T2SS	T3SS
Health Literacy	X			
Knowledge of Genetic Disease	X	X	X	X
Knowledge of Inherited Genetic Disease	X	X	X	X
PROMIS Anxiety/Depression	X	X	X	X
State Anxiety	X	X	X	X
Cancer Specific Distress	X	X	X	X
Uncertainty About Germline (i.e. inherited) Genetic Testing	X	X	X	X
Perceived Utility of Germline (i.e. inherited) Genetic Testing	X	X	X	X
Satisfaction with Genetic Counseling Services		X	X	
Regret and Disappointment Regarding Germline (i.e. inherited) Genetic Test Result			X	X
Communication about Germline (i.e. Inherited) Genetic Test Results			X	X

A. Descriptions of individual measures are included in Section [5.5](#). All instruments will be included as a single survey for each timepoint.

Rev. 7/17 7. Statistical Considerations

Rev. Add6

The primary objective of the primary Intervention Study (RCT, Step 1) is to evaluate the efficacy of web-based pre-disclosure genetic education (i.e. before receipt of tumor profile results) on knowledge (genetic knowledge and knowledge of test benefits and limitations) and distress (anxiety, depression and cancer specific worry) compared to usual care services in patients undergoing tumor profiling for advanced cancer. The primary analysis will, thus, be based on patients who have survey data evaluable at both T0 (baseline) and T1 (post-genetic education) (or T2, post-disclosure of test results). Given the survey completion rate for both T0 and T1 is approximately 60% (as analyzed in May 2018), the accrual goal of the primary intervention study needs to be increased from 400 to 670 patients in order to maintain sufficient power for evaluating the effect of web-based pre-disclosure genetic education.

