With the completion rate for both T0 and T1 surveys at approximately 60% (as analyzed in May 2018) and the goal of evaluable sample size at 200/arm (at least for the analysis of changes between T0 and T1), the accrual goal of the primary intervention study needs to be inflated from 400 to 670 patients in order to maintain sufficient power for detecting proposed changes from T0 to T1 and changes in knowledge and cancer specific from T0 to T2 (as described in the preceding paragraph). With the completion rate for both T0 and T2 surveys at approximately 45% (as analyzed in May 2018), the projected evaluable sample size of 150 patients/arm can give the power of 72% for changes in knowledge and 95% for changes in cancer specific distress from T0 to T2. These 670 patients will be randomized 1:1 between the two arms, and the randomization will be stratified by gender, race, age (> 65 vs. ≤ 65), and education level. As of this analysis time, 320 patients have been enrolled into the primary intervention study. The current COMET accrual rate is approximately 15 patients per month (based on the last 3 months). Assuming 15, 20 or 25 patients per month (as more expansion sites are added over time) can be accrued to COMET from the select sites, it is expected to take 23, 17 or 14 additional months, respectively, to complete Step 1 accrual of 670 patients.

The original accrual plan posed a limitation on White patients at 80% of the accrual goal to ensure diversity of patients. Given that the accrual of this study might terminate early if the funding of this study ends, the accrual limitation on White patients is being lifted to ensure the maximal number of patients enrolled before funding ends.

Power for various sample sizes

Variable	Change score time period	Sample Size Per Arm	Power for p< 0.005, 2-sided	Change Score Group 1	Change Score Group 2	Standard Deviation Group 1	Standard Deviation Group 2
State Anxiety	T0 to T1	100	98%	2.71	-2.78	8.24	7.43
State Anxiety	T0 to T1	150	100%	2.71	-2.78	8.24	7.43
State Anxiety	T0 to T1	200	100%	2.71	-2.78	8.24	7.43
State Anxiety	T0 to T1	300	100%	2.71	-2.78	8.24	7.43
State Anxiety	T0 to T1	400	100%	2.71	-2.78	8.24	7.43
State Anxiety	T0 to T1	61	85%	2.71	-2.78	8.24	7.43
IES-Total	T0 to T1	100	100%	0.29	-1.78	1.70	3.19
IES-Total	T0 to T1	150	100%	0.29	-1.78	1.70	3.19
IES-Total	T0 to T1	200	100%	0.29	-1.78	1.70	3.19
IES-Total	T0 to T1	300	100%	0.29	-1.78	1.70	3.19
IES-Total	T0 to T1	400	100%	0.29	-1.78	1.70	3.19

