7.1.2 Analysis Plan

Outcome change scores (primary endpoints) between time points for each study participant will be calculated. Two-sample T-tests will be conducted first to evaluate whether there is any difference in outcome change scores (with respect to the primary endpoints) between MATCH patients and non-MATCH patients. If differences are observed, the analysis described below will be performed separately for each cohort.

Two-sample T-tests assuming unequal variances will be used for the primary analyses of the change scores between arms. An intention-to-treat approach will be used in which the effect between randomized arms is evaluated, regardless of any treatment crossover. In secondary analyses of the primary endpoints, demographic characteristics between the two arms will be evaluated using T-tests and Fisher's Exact Tests to investigate if the arms were unbalanced with respect to potential confounders. If any potential confounders (in particular age, race/ethnicity and health literacy) are found to have means/proportions that are different between the arms at a p-value of less than 0.1, we will examine the treatment effect in multiple linear regressions of the outcomes in which the randomized arms will be included as a binary (0/1) dummy indicator and all potential confounders that have a p-value < 0.1 will be included as covariates. These analyses will be repeated using the as-treated approach in which we compare differences between the interventions the patient actually received (for example, patients were randomized to the on-line pre-disclosure genetic education but instead received usual care).

There is no plan to perform interim outcome monitoring for this study. Participating patient will be at minimal risk given the nature of the study. The study will be closely monitored for feasibility (Section [7.1.4](#)), and if feasible, information/data gathered would be useful and informative in patient care.

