7.1.3 *Exploratory analysis* will be longitudinal changes in cognitive (e.g. genetic knowledge), affective (cancer specific distress, state anxiety, general anxiety and general depression, perceived utility, uncertainty). In these analyses, multiple linear or logistic regressions will be fit to investigate temporal changes in the randomization arm effect, using the Generalized Estimating Equations (GEE) to account for correlated data over time. Unstructured working correlation matrices for GEE will first be considered unless there are model convergence problems, in which case exchangeable working correlation matrices will be used instead. In the regressions, survey wave and the randomized arm will be included as dummy indicator (0/1 variables) covariates. As there are four survey time points, we include three dummy indicators for T1, T2 and T3. In analyzing the change of scores (T1-T0, T2-T0, T3-T0), two dummy indicators will be needed. We will also include interactions between the survey wave indicators and the arm indicator to see if the arm effect changes over time. We will also include potential baseline confounding variables that were not balanced between arms at a p-value < 0.1 (using T-Tests and Fisher's Exact Tests). These analyses will be repeated using the as-treated approach as well.

To evaluate potential moderators as described in Section [2](#), we will add relevant interaction terms to the GEE-estimated multiple linear and logistic regressions described above. Of most interest are interactions between the potential moderators (e.g. test result, sociodemographic factors, health literacy, baseline knowledge or distress) and the arm indicator.

Other exploratory endpoints include satisfaction and regret/disappointment related to tumor genetic test results, and how to better deliver tumor genetic test results and germline information in the future. Summary statistics will be provided and comparison may be explored between arms using T-Tests or Fisher's Exact Tests at two-sided significance level of 0.05.

Rev. 7/17

7.1.4 *Feasibility*

Monitoring enrollment on the primary study:

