Accrual will be closely monitored after the addendum expanding eligibility criteria activates. A formal evaluation will start at 6 months after the addendum expanding eligibility criteria activates, allowing some time for the select sites to get ready for enrolling patients. If the rate of enrollment on Step 1 of EAQ152 is < 5 patients per month, the data will be discussed with the study team and the NCI to reevaluate the feasibility of the study.

Monitoring rate of compliance and questionnaire response:

Primary analysis will be based on randomized arms. Patients who have survey data at T0, and at least one of the follow-up timepoints

Rev. 2/17

(T1 or T2), will be considered as evaluable. Among the first 100 patients who are enrolled on Step 1 for the primary study, if proportion of evaluable patients is < 60%, the data will be discussed with the study team and the NCI to re-assess the feasibility. Proportion of patients who cross-over, and proportion of the patients on Arm A who complete the web-based education, will also be reported.

7.2 Secondary Germline Genetic Testing & Counseling Substudy (Step 2 – Arm D and Arm E)

Rev. 7/17

7.2.1 The *primary endpoints* for the substudy will be uptake of remote genetic counseling and uptake of clinical germline testing.

This substudy will be exploratory in nature. We will evaluate, separately, the proportion of individuals who complete a) remote genetic counseling and b) germline testing, among patients (whose hospital sites open accrual to COMET Step 2) with a **potential** clinically significant incidental germline mutation identified through MATCH or non-MATCH tumor profiling. The current COMET Step 2 accrual rate through MATCH is 1-2 patients per month. The substudy will stop patient accrual either when the accrual goal of 100 patients is met or 4 months after the primary study is closed to accrual (allowing the tumor profiling results to be returned back to the sites and so any remaining qualifying patients can be enrolled into the substudy), whichever is earlier.

Rev. 7/17

7.2.2 *Analysis Plan*

The proportions of individual uptake of remote genetic counseling and uptake of clinical germline testing will be calculated separately, along with the 95% confidence intervals.

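### The ten primary tests leave out about 40% (T1) and 55% (T2) of randomized patients; the only planned analysis using partial follow-up is exploratory, and none covers non-response that depends on unobserved scores

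*Combined protocol and SAP*

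**What the plan says.** The opening of section 7 defines the analysis set: "The primary analysis will, thus, be based on patients who have survey data evaluable at both T0 (baseline) and T1 (post-genetic education", with T2 as the alternative follow-up. Section 7.1.1 names ten primary comparisons (five outcomes, each as change from T0 to T1 and from T0 to T2), tested at two-sided 0.005. Section 7.1.2 tests each patient's change score with an unequal-variance t-test.

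Section 7.1.1 puts T0+T1 completion at about 60% in May 2018 and raises accrual from 400 to 670 in response. For the later contrast it says "With the completion rate for both T0 and T2 surveys at approximately 45" percent, projecting 150 evaluable patients per arm with 72% power for knowledge and 95% for cancer-specific distress. On timing: "As of this analysis time, 320 patients have been enrolled into the primary intervention study".

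The provisions that bear on missing surveys are:

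- **Intention-to-treat (7.1.2):** "An intention-to-treat approach will be used in which the effect between randomized arms is evaluated, regardless of any treatment crossover".
- **Secondary regressions (7.1.2):** baseline variables that differ between arms are added, so that "all potential confounders that have a p-value < 0.1 will be included as covariates".
- **Cohort rule (7.1.2):** after a MATCH versus non-MATCH comparison, "If differences are observed, the analysis described below will be performed separately for each cohort".
- **Exploratory longitudinal model (7.1.3):** arm-by-wave regressions "using the Generalized Estimating Equations (GEE) to account for correlated data over time", with an unstructured working correlation tried first.
- **Evaluability for feasibility monitoring (7.1.4):** "Patients who have survey data at T0, and at least one of the follow-up timepoints" (T1 or T2) count as evaluable.
- **Data collection (4.3, 5.4):** patients without T0 go off study. Late surveys prompt e-mail reminders and possibly a telephone call, and nothing further after that.

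**The concern.** A change score needs both surveys, so each test compares the responders in one arm with the responders in the other. The intention-to-treat sentence deals with crossover and says nothing about randomized patients who lack a score. The 7.1.4 evaluability rule does not supply the missing half of a pair.

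Raising accrual to 670 restores the number of pairs at T1. It does not restore comparability if the patients who answer are selected differently in the two arms. T2 follows disclosure of tumor results in patients with advanced cancer, so willingness to answer could plausibly relate to distress or understanding, which are the outcomes themselves. The T2 tests also ignore T1 answers from patients who then missed T2, although T2 knowledge is the contrast with only 72% power. Without a planned sensitivity analysis, a reader cannot judge how strong selective non-response would have to be to overturn a result.

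**Working it through.** **1. Reproduce the plan's figures.** The per-test level is 0.05/10 = 0.005, so z = 2.807. 400/0.60 = 667, against 670 stated. 670 × 0.60/2 = 201 per arm, against 200. 670 × 0.45/2 = 151 per arm, against 150. The rates therefore apply to all randomized patients.

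Power for T0-T2 knowledge at 150 per arm: d = (5.86 − 4.40)/√((4.30² + 3.05²)/2) = 1.46/3.73 = 0.39. Power = Φ(0.392 × √75 − 2.807) = 72%, as stated. For IES, d = 1.17/2.29 = 0.51 and power is 95%, as stated.

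**2. Patients left out.** T0-T1 tests: 670 × 0.40 = 268. T0-T2 tests: 670 × 0.55 = 368.5, about 369. Both counts include T0 non-completers. They left before any education, because Arm A receives its access code only after T0 (5.2.1). Their number is not given.

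**3. T1 answers unused at T2.** T0+T1 without T2 equals 0.60 minus the share with all three surveys. That share lies between 0.60 + 0.45 − 1 = 0.05 and 0.45, so the unused share is 15% to 55%. The minimum, 670 × 0.15 = about 100 patients (320 × 0.15 = 48 in May 2018), requires that every T2 completer also completed T1. The overlap is not stated. The 45% may also count patients not yet due for T2, in which case the final T2 rate would be higher and these numbers lower.

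**4. Illustrative bias; all selection inputs are assumed.**

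- *Mild case.* If responders and non-responders differ by 0.2 to 0.5 SD in both arms and completion differs by 10 points, bias = 0.10 × 0.2 to 0.10 × 0.5 = 0.02 to 0.05 SD, and rejection is 0.6 to 1.1%. Equal selection with equal completion gives no bias.
- *T2 response depends on the T1 score in one arm only.* Assume no true effect, 75% T2 response among T0+T1 completers (0.45/0.60, the minimum case in step 3), and a logistic slope of 0.5 or 1.0 per SD. Responders' mean T1 score then shifts by 0.120 or 0.213 SD. Multiplying by a T1-T2 correlation of 0.4 or 0.8 gives the T2 bias. With SE = √(2/150) = 0.115:

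| Slope | Correlation | Bias (SD) | Rejection at nominal 0.5% |
|---|---|---|---|
| 0.5 | 0.4 | 0.048 | 0.9% |
| 0.5 | 0.8 | 0.096 | 2.4% |
| 1.0 | 0.4 | 0.085 | 2.0% |
| 1.0 | 0.8 | 0.171 | 9.2% |

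Simulation of these cases gave 0.8 to 10.2% for the Welch test. A joint likelihood estimator had bias within 0.003 SD and rejection of 0.3 to 0.5%. A GEE of the 7.1.3 type with equal SDs had bias of at most 0.004 SD and rejection of 0.3 to 0.7%.

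**5. Where the GEE is less secure.** A second simulation had no true effect, 45% T2 response, T1 seen in everyone, slopes of 0.5 in size and correlations of 0.4 to 0.6. With the printed arm SDs and response depending on T1, GEE bias reached 0.06 SD for knowledge and 0.17 SD for state anxiety. Those maxima arose with the same slope in both arms. With response depending on the unobserved T2 score, GEE bias was 0.03 to 0.24 SD for a slope in one arm only and 0.31 to 0.43 SD for opposite slopes.

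**6. Tipping point if the planned effect is observed.** Shift = (d − 2.807 × SE)/share missing, with SE held fixed. T2 knowledge: (0.392 − 0.324)/0.55 = 0.12 SD (0.46 points). T2 IES: (0.510 − 0.324)/0.55 = 0.34 SD. T1 knowledge, at 200 per arm with d = 0.66: (0.664 − 0.281)/0.40 = 0.96 SD. The T2 figures are lower bounds, because they treat all 55% as imputed. If, say, 30% never completed T0, the share falls to 1 − 0.45/0.70 = 0.357 and T2 knowledge tips at 0.19 SD. Excluding patients who never received results raises it further.

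**7. Gain at T2.** With 200 at T1 and 150 at T2 per arm (again the minimum case in step 3), the variance factor is 1 − 0.25ρ². For ρ = 0.4, 0.6 and 0.8, effective n is 156, 165 and 179, and knowledge power is 74%, 77% and 81%, against 72%.

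**The case against.** The strongest reply is that the plan already contains a longitudinal analysis. The 7.1.3 GEE has arm-by-wave terms and tries an unstructured correlation first, so it borrows T1 data for patients who miss T2. In step 4 it removed nearly all the bias. A reader might infer that nothing planned deals with non-response related to post-baseline scores; the documents do not support that. What remains is that this model is exploratory, is not offered as a missing-data analysis, does not feed the ten primary conclusions, and has no general missing-at-random guarantee (step 5).

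A reader might also infer that the primary results are biased. The documents give no completion rates by arm and describe no arm-specific mechanism. The T1 link goes to everyone 7 days after T0, Arm A patients who never open the site are still surveyed (4.1.6), and reminders are the same in both arms. Some of the loss precedes any education. The one-arm scenario is therefore an assumption, and the mild case is not alarming.

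Finally, replacing ten prespecified tests after 320 enrolments is partly an efficiency choice. That is fair, so the fix allows the Welch tests to stay primary. It does not answer the absence of any analysis for dependence on unobserved scores.

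**Conclusion.** The point holds in this limited form. Each primary test uses one complete pair, leaving out about 268 (T1) and 369 (T2) of 670 at the May 2018 rates. The only planned analysis that uses partial follow-up is exploratory and unweighted, and none addresses non-response driven by unobserved scores. Bias is possible but not demonstrated, and its direction is unknown.

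The 0.05 to 0.17 SD illustration depends on the assumed one-arm dependence, slopes, correlations and 75% conditional response. The planned T2 effects, 0.39 SD for knowledge and 0.51 SD for IES, give the scale. T1 conclusions look sturdy at the planned effects. T2 knowledge is more fragile, with a tipping shift of at least 0.12 SD. The 74 to 81% power range holds only if every T2 completer also completed T1. This should be changed, with medium confidence.

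**What to change.** **In 7.1.2:**

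1. Estimate the T1 and T2 arm contrasts, at two-sided 0.005, from one likelihood-based repeated-measures model per outcome. Include arm-by-time, baseline-by-time and the stratification factors, and use all randomized patients with T0 and any follow-up. Fit it within cohort where the MATCH/non-MATCH rule calls for separate analysis.
2. Keep the Welch tests as a labelled complete-case analysis. If the sponsor prefers them as primary, prespecify the model as a sensitivity analysis of all ten comparisons.
3. Add delta-adjusted multiple imputation for T0 completers with missing T1 or T2. Increase the between-arm shift until each significant result tips or the limit of the scale's range is reached. Do not impute T2 for patients who never received tumor results, since T2 is triggered by that receipt (5.2.1).
4. Report T0, T1 and T2 completion, and the number never given results, by arm.

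**Cost:** plan wording and modest extra programming on data already collected, with no change to enrolment, randomization or surveys. The model itself assumes missing at random and gains mainly at T2, which is why item 3 is needed as well.

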1.2 Hypotheses

1. The provision of web-based genetic education prior to receipt of tumor profiling results will be associated with greater increases in genetic knowledge and less increase in distress (Primary Intervention Study : RCT)
2. Participant factors, suggested by the Self-Regulation Theory of Health Behavior (SRTHB; e.g. test result, sociodemographic factors, health literacy, baseline knowledge or distress) will identify subgroups of patients who benefit more or less from the intervention (web-based pre-disclosure genetic education). (Primary Intervention Study: RCT)
3. The majority of participants with **potential** incidental germline mutations identified through tumor profiling will be willing to participate in: a) remote genetic counseling and b) genetic testing for **potential** germline mutations. (Secondary Genetic Counseling Substudy)
4. The uptake of remote counseling and testing among advanced cancer patients with **potential** germline incidental findings will be associated with patient factors (e.g. distress, uncertainty, family history, etc.) predicted by the Self-Regulation Theory of Health Behavior (SRTHB). Additionally, we hypothesize that remote pre- and post-test counseling with a genetic counselor will be associated with increases in knowledge, decreases in uncertainty and distress and increases in communication to at-risk relatives. (Secondary Genetic Counseling Substudy)

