While the original education was delivered via a health educator, this approach was chosen to maximize patient feedback regarding key elements and content. We had originally envisioned that it could be adapted for delivery by alternative modalities (e.g. print, web), if acceptable to patients. As an example, in the ongoing RESPECT study (R01-CA190871:[name]), we have adapted provider-mediated tiered-binned pre-disclosure counseling for return of individual research results to an on-line genetic education followed by remote counseling with a genetic counselor at the time of result disclosure to address patient burdens associated with in-person visits. The ongoing multi-site RESPECT study will evaluate the outcomes of receipt of individual germline research results with this alternative delivery model.

To date, 25 breast cancer patients have enrolled in the COMET pilot study. 20 have completed genetic education and post-education

surveys. 14 have received results and have completed post-disclosure surveys.

Key preliminary findings relevant to this proposal include:

1. Many patients reported a limited understanding of the difference between germline and somatic genetics and the limitations of tumor profiling (e.g. the potential for no druggable targets).
2. Participants reported greater interest in web-based administration as an alternative to provider-mediated counseling than print materials. Patients reported advantages to web-based education included convenience, the ability to revisit information, faster access and the individual ability to select information to view. Many reported no disadvantages to a web-based alternative, while some identified losing the personal interaction, getting confused or not knowing what to view on a website.
3. Preliminary data suggests pre-disclosure genetic education may be associated with increases in knowledge and decreases in depression and general and state anxiety from baseline to post-disclosure.

In this pilot, there was no comparison arm, so changes in these outcomes need to be evaluated in a randomized study.

1.5.2 Secondary Genetic Counseling Substudy - Genetic Counseling for Incidental Germline Findings (Step 2):

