As MATCH has approached its goal of sequencing ~6000 patient tumors, this section incorporates changes to expand eligibility criteria (effective since Addendum #3) to allow patients from select sites who potentially undergo tumor profiling through non-MATCH assays and to increase the accrual goal (effective since Addendum #6). In this section, patients who enter COMET through MATCH Step 0 (prior to or after the activation of this addendum allowing for eligibility expansion) will be referred as the MATCH cohort, and other patients (who enter after the corresponding addendum activates) will be referred as the non-MATCH cohort.

7.1 Primary Study: Randomized Study of Web-based Pre-disclosure Genetic Education versus Usual Care (Step 1 – Arms A & B)

Rev. 2/17

NOTE: Patients on Arm C (see Section [□□□□](#)) will not participate in or complete any primary study (Step 1) education or surveys, and will immediately be registered to Arm E and complete all of the substudy (Step 2) procedures.

Rev. 7/17

7.1.1 *Primary endpoints* will include change in knowledge and distress (state anxiety, Promis anxiety, Promis depression and cancer specific distress) from baseline to post-education (T0 to T1) and baseline to post-disclosure (T0 to T2).

The following 10 analyses are of primary interest: change scores from T0 to T1, and T0 to T2 of each of the following five outcomes: knowledge, state anxiety, cancer specific distress, Promis anxiety and Promis depression, which correspond to 10 primary analyses. To account for the 10 primary analyses, A Bonferroni correction is considered here, setting the nominal p-value to declare statistical significance of $p < 0.005$ (5% Typical Type I error rate / 10 comparisons = 0.5% nominal p-value for declaring statistical significance). Preliminary data from the COMET pilot study (State Anxiety, IES-Total, Knowledge) is used to calculate power. As there was no preliminary data for Promis Depression/Anxiety in a similar setting, power calculation for these two measurements are based on data reported in Hinds et al. (2012). A sample size of 200 (with evaluable paired data) /arm is chosen here, which provides at least 85% power for all short-term outcomes (e.g. T0-T1) and changes in knowledge and cancer specific distress after receipt of tumor profiling results (e.g. T0-T2), using t test at two-sided 0.005 significance level.

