IES-Total	T0 to T1	46	85%	0.29	-1.78	1.70	3.19
Knowledge	T0 to T1	100	97%	1.70	-1.50	6.11	3.02
Knowledge	T0 to T1	150	100%	1.70	-1.50	6.11	3.02
Knowledge	T0 to T1	200	100%	1.70	-1.50	6.11	3.02
Knowledge	T0 to T1	300	100%	1.70	-1.50	6.11	3.02
Knowledge	T0 to T1	400	100%	1.70	-1.50	6.11	3.02
Knowledge	T0 to T1	68	85%	1.70	-1.50	6.11	3.02
State Anxiety	T0 to T2	100	13%	-2.43	5.00	4.04	14.58
State Anxiety	T0 to T2	150	23%	-2.43	5.00	4.04	14.58
State Anxiety	T0 to T2	200	34%	-2.43	5.00	4.04	14.58
State Anxiety	T0 to T2	300	55%	-2.43	5.00	4.04	14.58
State Anxiety	T0 to T2	400	72%	-2.43	5.00	4.04	14.58
State Anxiety	T0 to T2	512	85%	-2.43	5.00	4.04	14.58
IES-Total	T0 to T2	100	79%	-1.00	-2.17	1.53	2.86
IES-Total	T0 to T2	150	95%	-1.00	-2.17	1.53	2.86
IES-Total	T0 to T2	200	99%	-1.00	-2.17	1.53	2.86
IES-Total	T0 to T2	300	100%	-1.00	-2.17	1.53	2.86
IES-Total	T0 to T2	400	100%	-1.00	-2.17	1.53	2.86
IES-Total	T0 to T2	114	85%	-1.00	-2.17	1.53	2.86
Knowledge	T0 to T2	100	48%	5.86	4.40	4.30	3.05
Knowledge	T0 to T2	150	72%	5.86	4.40	4.30	3.05
Knowledge	T0 to T2	200	86%	5.86	4.40	4.30	3.05
Knowledge	T0 to T2	300	98%	5.86	4.40	4.30	3.05
Knowledge	T0 to T2	400	100%	5.86	4.40	4.30	3.05
Knowledge	T0 to T2	194	85%	5.86	4.40	4.30	3.05

Power for Promis Depression and Promis Anxiety

With 200 evaluable patients per arm, there is 91% power to detect an effect size of 0.33 (as fraction of standard deviation), using t-test at two-sided significance level 0.005. Based on data from 92 children/adolescents, Hinds et al. (2012) reported standard deviation of 10.74 for Promis Depression and 12.5 for Promis Anxiety, respectively. Assuming the standard deviations for these two measurements in our proposed study are similar, the following table gives the absolute difference that can be detected with 91% power, under different assumptions for the correlation between the measurements across two timepoints, at two-sided significance level 0.005.

Variable	Correlation	Standard deviation of change	Effect size (as fraction of standard deviation)	Absolute difference	Power
Promis Depression	0.4	11.8	0.33	3.89	91%
Promis Depression	0.6	9.6	0.33	3.17	91%
Promis Depression	0.8	6.8	0.33	2.24	91%
Promis Anxiety	0.4	13.7	0.33	4.5	91%
Promis Anxiety	0.6	11.2	0.33	3.7	91%
Promis Anxiety	0.8	7.9	0.33	2.6	91%

Rev. 7/17

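### Improvement, not an error: Holm's step-down procedure over the ten primary tests keeps the 5% family-wise error and never rejects less than the fixed 0.005 rule

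*Combined protocol and SAP*

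**What the plan says.** Section 7.1.1 takes five outcomes (knowledge, state anxiety, cancer-specific distress on the IES, PROMIS anxiety, PROMIS depression) over two periods (T0-T1 and T0-T2), "which correspond to 10 primary analyses". On multiplicity: "A Bonferroni correction is considered here, setting the nominal p-value to declare statistical significance of" p < 0.005, that is 5%/10. Section 7.1.2 specifies unequal-variance two-sample t-tests for these comparisons and adds no step-down or other sequential rule.

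The design aimed for 200 evaluable patients per arm, to give at least 85% power for all T0-T1 outcomes and for knowledge and cancer-specific distress at T0-T2. With T0+T2 survey completion at about 45%, section 7.1.1 accepts less: "the projected evaluable sample size of 150 patients/arm can give the power of 72% for changes in knowledge".

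Section 7.1.2 also provides for testing whether change scores differ between MATCH and non-MATCH patients. On that it says: "If differences are observed, the analysis described below will be performed separately for each cohort".

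**The concern.** Nothing here is invalid. The point is that a rule with the same error guarantee is available and is at least as powerful on every data set. Holm orders the ten p-values and compares them with 0.05/10, 0.05/9, ..., 0.05/1, stopping at the first failure. No threshold is below 0.005, so every Bonferroni rejection is also a Holm rejection.

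The choice has some practical weight. Knowledge is half of the primary objective, its T0-T2 power has slipped from the planned 85% to 72%, and section 7.1.1 warns that accrual may stop early if funding ends. A gain that costs no patients is useful here. How large it is depends on how many of the other nine tests reject.

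**Working it through.** **Inputs (section 7.1.1 power table).** T0-T1 at 200 per arm; T0-T2 at 150 per arm. Noncentrality = difference / sqrt((SD1² + SD2²)/n).

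- Knowledge T0-T1: 3.20, SDs 6.11 and 3.02, gives 6.64
- State anxiety T0-T1: 5.49, SDs 8.24 and 7.43, gives 7.00
- IES T0-T1: 2.07, SDs 1.70 and 3.19, gives 8.10
- Knowledge T0-T2: 1.46, SDs 4.30 and 3.05, gives 1.46/0.4304 = 3.39
- IES T0-T2: 1.17, SDs 1.53 and 2.86, gives 4.42
- State anxiety T0-T2: the printed means (difference 7.43, SDs 4.04 and 14.58) give 6.01; the printed 23% power corresponds to 2.08. Both were run.
- PROMIS: 0, or 0.33 SD, which gives 3.30 at T1 and 2.86 at T2. The plan gives 0.33 only as a detectable effect.

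The documents give no correlation between endpoints, so a common value of 0, 0.3 or 0.5 was assumed.

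**The plan's own figure.** Knowledge T0-T2 at two-sided 0.005: Φ(3.39 − 2.807) = 72.1% (Welch t 71.2%; printed 72%).

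**Single-test power at the Holm thresholds.** 0.05/9: 73.2%. 0.05/8: 74.5%. 0.05/7: 75.9%. 0.05/6: 77.4%. 0.05/5: 79.3%. If the four other well-powered pilot effects reject first, knowledge T0-T2 is tested at 0.05/6 = 0.00833, a gain of about 5 points.

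**Simulation of the full procedure** (300,000 sets of ten z-statistics per scenario). Knowledge T0-T2 is 72% under Bonferroni throughout.

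| Real effects | Holm |
|---|---|
| Knowledge T0-T2 only | 72% |
| Both knowledge effects | 73% |
| Both knowledge effects + state anxiety T0-T2 (2.08 or 6.01) | 73-75% |
| Both knowledge effects + IES T0-T2 | 74-75% |
| Three T0-T1 pilot effects + IES and knowledge T0-T2 (five effects) | 77-78% |
| Five effects + state anxiety T0-T2 at 2.08 | 78% |
| Five effects + state anxiety T0-T2 at printed means | 79% |
| Five effects + PROMIS at T1, without or with state anxiety T0-T2 | 80-83% |
| Five effects + PROMIS at both times, without or with state anxiety T0-T2 | 82-88% |

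With all effects halved, 13% stays at 13% when this is the only effect and reaches at most 20% in the fullest scenario. No replicate was rejected by Bonferroni and not by Holm. The highest Holm family-wise error was 4.8%.

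**Equivalent in patients.** At fixed 0.005, power of 73%, 74.5% and 77.5% needs n = (2.807 + z)² × (4.30² + 3.05²)/1.46² = 152.5, 156.6 and 165.5 per arm. At 45% completion that is (152.5 − 150) × 2/0.45 ≈ 11, then about 29 and 69, extra registrations. Power of 85% needs about 193 per arm.

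**Separate cohorts.** Splitting makes 20 tests. With no effects anywhere, the chance of any false rejection is 9.5%, 8.9% and 7.7% (correlation 0, 0.3, 0.5), both for fixed 0.005 and for Holm within cohort; the bound is 20 × 0.005 = 10%. Holm over all 20 gives 4.9%, 4.6% and 4.1%. Assuming half the patients in each cohort, power for knowledge T0-T2 in one cohort is 34% at fixed 0.005, 35-40% with Holm within cohort, 28-32% with Holm over 20 and 27% with Bonferroni over 20. The lower Holm figures assume only the knowledge effects are real, the upper that all five pilot effects hold.

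**The case against.** The best counter-argument is that this is a preference. The plan states ten tests, one threshold and the resulting 72%. Under a fixed threshold each endpoint stands on its own p-value, whereas under Holm the verdict on knowledge can depend on the anxiety results. That is a real difference in interpretation, but it gives no protection against false positives that Holm lacks.

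The gain is also small where the hypotheses are coherent. Hypothesis 1 in section 1.2 expects that education "will be associated with greater increases in genetic knowledge and less increase in distress". In the power table, group 1 does better on knowledge at both times and on state anxiety T0-T2 (−2.43 vs 5.00), but worse on state anxiety T0-T1 (2.71 vs −2.78), IES T0-T1 (0.29 vs −1.78) and IES T0-T2 (−1.00 vs −2.17). Whichever group is education, these cannot all agree with the hypothesis. Keeping only the effects that agree in direction with knowledge T0-T2 gives 73-75%. The pilot is thin too: "14 have received results and have completed post-disclosure surveys", and "In this pilot, there was no comparison arm, so changes in these outcomes need to be evaluated in a randomized study". This stands, and the larger gains should be read as illustrations.

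The range of 0 to 6 points covers the five effects plus state anxiety T0-T2 at its printed 23% power. At its printed means the gain is about 7. Those means imply 99.9% power at 150 per arm, so the table row conflicts with itself. The PROMIS statement has a similar problem: "there is 91% power to detect an effect size of 0.33 (as fraction of standard deviation" at two-sided 0.005, where the calculation gives about 69%; 91% matches alpha 0.05. Both need reconciling separately, and neither is a reason to adopt Holm.

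Finally, Holm does not solve the cohort split, and applied over 20 tests it has less power than the present rule per cohort. That is correct: the guarantee of never rejecting less applies to an unchanged family of tests.

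**Conclusion.** The point holds as an improvement. Over the same ten tests Holm keeps 5% family-wise error under any dependence and cannot lose a rejection; neither property depends on the pilot data. For knowledge T0-T2 at 150 per arm the gain over 72% is 0 to 6 points unless further effects exist, and 1 to 3 points if the real effects are those that agree in direction. It recovers part of the shortfall from 85%, and closes it only in some scenarios with PROMIS effects at both times.

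The sizes rest on the printed means and SDs, assumed correlations of 0 to 0.5, assumed PROMIS effects of 0 or 0.33 SD and, for separate cohorts, an assumed equal split.

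**What to change.** In section 7.1.1, replace the fixed p < 0.005 rule with one paragraph stating four things:

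1. Holm's procedure is applied to the ten primary p-values at family-wise two-sided 0.05.
2. Holm-adjusted p-values are reported.
3. The planning power stays at 0.005 per test, as a conservative figure.
4. If section 7.1.2 leads to separate cohort analyses, the family is defined in one of two ways. Either Holm covers all 20 tests, which holds 5% trial-wide but has less power than the current 0.005 per cohort. Or Holm is applied within each cohort, with a statement that 5% then holds per cohort only and up to about 10% trial-wide, as with the current rule.

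The cost is a reviewed protocol amendment, with no extra patients or data. It must be final before anyone setting the rule has seen outcomes by arm, and must say so: the absence of planned interim monitoring does not establish this, and 320 patients were already enrolled when the accrual goal was revised. The one technical drawback is that simultaneous confidence intervals matching Holm are less simple, but the plan promises none for these endpoints.
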